6. STUDY ASSESSMENTS

6.1. Efficacy Assessment

6.1.1. Pain Intensity Assessment

- Pain intensity scores measured using NRS as "How much pain are you experiencing right now?" * will be assessed as follows:
 - Upon arrival in the Post-Anesthesia Care Unit (PACU)
 - At 15-minute intervals in the PACU
 - At to PACU discharge
 - Every 6 hours from the end of surgery to 96 hours postsurgery as follows: 6 h, 12 h, 18 h, 24 h, 30 h, 36 h, 42 h, 48 h, 54 h, 60 h, 66 h, 72 h, 78 h, 84 h, 90 h, and 96 h.
 - Prior to administration of any pain medication until 96 hours post-surgery
- Pain intensity using the NRS once daily at 21:00 (±3 h) from POD 1 to POD 14 measured as "What was your **worst** pain in the last 24 hours?"
- Pain intensity using the NRS once daily at 21:00 (±3 h) from POD 1 to POD 14 measured as "What was your **average** pain in the last 24 hours?"

* If subject is asleep, the subject will not be awakened to assess pain. If the subject awakens within the time window, a pain score will be collected then.

6.1.2. Opioid Dose Conversion

Opioids dose will be converted to oral morphine equivalent dose (OMED mg) using the conversion factor in Table 5 for all summaries. Total opioid dose is the sum of all opioids in OMED taken during the time interval of interest.

Table 5. Conversion Factors to IV and Oral Morphine Equivalent Dose from Other Opioids											
Medication	Unit	Route	Oral Morphine Conversion (Multiplication) Factor								
Oxycodone, Oxycocet, Percocet, acetaminophen-oxycodone	mg	РО	1.5								
Morphine	mg	IV, IM, SC	3								
Morphine	mg	РО	1								
Hydromorphone (Dilaudid)	mg	IV, IM, SC	20								
Hydromorphone (Dilaudid)	mg	РО	4								
Fentanyl	mg	IV, PO, IM	300								

Table 5. Conversion Factors to IV and Oral Morphine Equivalent Dose from Other Opioids					
Medication	Unit	Route	Oral Morphine Conversion (Multiplication) Factor		
Hydrocodone combination product - Vicodin, Norco, Lorcet, Lortab, hydrocodone- acetaminophen, Ketobemidone	mg	РО	1		
Codeine combination product - Tylenol 3, acetaminophen-coedine, Paracetamol Forte, Tylenol 4	mg	РО	0.15		
Ultram, Tramadol, Tramacol hydrochloride	mg	PO, IM	0.25		
Demerol, Meperidine, Pethidine	mg	IV, SC	0.3		
Demerol, Meperidine, Pethidine	mg	РО	0.1		
Ketobemidone, Oxycodone	mg	IV	3		
Nalbuphine/Nallouphine (Nubain/Manfine)	mg	IV, IM, SC	3		
PO = oral, IV = intravenous, IM = Intramuscular, SC = subcutaneous.					

6.1.3. Subject Satisfaction with Pain Management

The subject's satisfaction with pain management will be collected at 96 hours post-surgery using question from the International Pain Outcome (IPO). Subjects will be asked to circle a number that best describes how satisfied they are with the results of their pain treatment since surgery on an eleven-point Likert scale from zero (extremely dissatisfied) to 10 (extremely satisfied).

6.1.4. Postsurgical Breakthrough Pain Medication

All opioid and other analgesics (pain medications) administered post-surgery through POD 14 will be recorded. Analgesics will be administered based on the pain assessment as outlined below.

- For the initial treatment of post-surgical pain, subjects may receive either acetaminophen or NSAIDs without exceeding the maximum daily dose.
- If the initial pain treatment (acetaminophen or NSAIDs) is insufficient for pain relief, immediate release PO oxycodone may be administered in a stepwise approach:
 - Initial dose of 5 mg oxycodone may be offered;
 - If the initial opioid dose is insufficient for pain relief, 10 mg oxycodone may be offered.

• If a subject is unable to tolerate PO medication or the PO oxycodone pain relief is insufficient, IV morphine (initiated at 2 mg) or hydromorphone (initiated at 0.2 mg) may be administered.

Post discharge, the subject will be provided with a prescription for oxycodone 5 mg. The subject may take acetaminophen, NSAIDs, or the prescribed oxycodone and will be given instructions on which medication to take PRN based on their pain intensity.

6.2. Pharmacokinetic assessments (Cohort 1 only)

Blood samples for PK assessment will be obtained from the Cohort 1 subjects. A total of 17 PK samples will be collected for each subject. These samples will be obtained at predose/baseline (up to 15 min before block), 30 min, 45 min, and 1 h, 2 h, 8 h, 12 h, 24 h, 30 h, 48 h, 60 h, 72 h, 84 h, 96 h, 120 h, 144 h, and 168 h from end of block procedure.

6.3. Pharmacodynamic Assessments (Cohort 1 only)

Time of onset/offset is collected on the corresponding "PD Assessment – Onset/Offset Sensory/Motor Block" eCRF.

6.3.1. Assessment of Sensory Block:

Sensory function for the sciatic and saphenous nerve will be assessed independently using a wooden tongue depressor and ice. This assessment will evaluate light touch and cold sensation.

Sensory function assessment will include the following four locations:

- 1. Saphenous proximal Medial aspect of the lower leg (3-4 cm below the knee)
- 2. Saphenous distal Medial aspect of the lower leg (3-4 cm above ankle)
- 3. Sciatic proximal Lateral aspect of the lower leg (3-4 cm above ankle)
- 4. Sciatic distal Sole of the foot

The tongue depressor application and ice will be performed at predose, 15 min, 30 min, 45 min, 1 h, 2 h, 8 h, 12 h, 24 h, 30 h, 48 h, 60 h, 72 h, 84 h, 96 h, 120 h, 144 h, and 168 h hours from the end of the nerve block procedure, or until full sensory function has returned to baseline (preblock) levels in two consecutive evaluations. Additional unscheduled assessments may be performed, particularly around the surgery if no onset of block is noted on the last scheduled assessment prior to surgery.

Onset of sensory block (sciatic and saphenous nerve tracked independently) will be defined as the earliest timepoint with loss of EITHER light touch sensation OR cold sensation in EITHER proximal OR distal locations at any time. If onset time is not achieved, it will be considered censored at the last onset assessment time prior to surgery. **Offset of sensory block** (sciatic and saphenous nerve tracked independently) will be defined as recovery of BOTH light touch

sensation AND cold sensation in BOTH proximal and distal locations on two consecutive recovery assessments (excluding Not Done assessment). After offset of all sensory assessments are noted (on 2 consecutive assessments for all 4 locations), no subsequent assessments will be conducted. If offset time is not achieved, it will be considered censored at the last offset assessment time after surgery. If the patient's sensory block is recovered at the last assessment to confirm, the sensory block is considered recovered at this last time point. **Duration of sensory block** will be defined as the time between onset and offset of the sensory blocks for each nerve individually. If onset is not achieved, duration will be calculated from the surgery start time through the offset time, left censored. If both onset and offset assessment time, interval censored. See Section 9.5.2.4 for how the censoring is handled in the analysis. If postdose onset assessments are completely missing, time to onset will be set to missing.

6.3.2. Assessment of Motor Block:

Motor function (onset and offset of motor block) will be assessed using the 2-point scale on the side of the block. This will be used to determine the onset and duration of motor blockade.

Motor function will be assessed using a 2-point scale. The motor function test will be performed at predose, 15 min, 30 min, 45 min, 1 h, 2 h, 8 h, 12 h, 24 h, 30 h, 48 h, 60 h, 72 h, 84 h, 96 h, 120 h, 144 h, and 168 h from end of block procedure, or until full motor function has returned to pre-dose levels in two consecutive evaluations. Additional unscheduled assessments may be performed, particularly around the surgery if no onset of block is noted on the last scheduled assessment prior to surgery.

Onset of motor block will be defined as the earliest timepoint with 2-point score of 1- Partial or no foot movement as opposed to 0- Complete foot movement. If subject does not experience loss of motor, their onset will be censored at their last available motor assessment time point prior to surgery. **Offset of motor block** will be defined as resolution of motor block at foot, first time point of the two consecutive recovery assessments (score 0- complete foot movement) (excluding Not Done assessment). If offset time is not achieved, it will be considered censored at the last offset assessment time after surgery. After offset of motor block is noted (on 2 consecutive assessments), no subsequent assessments will be required. If the patient's motor block is recovered at the last assessment to confirm, the motor block is considered recovered at this last time point. **Duration of motor block** will be defined as time between onset and offset of motor block. The censoring and missing data rule for the duration of sensory block also applies to the duration of motor block.

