
Cohort 2: Efficacy and Safety
		

The participants enrolled in Cohort 2 will provide measures for efficacy and safety. About 60 subjects will be enrolled in this cohort. On day of surgery, eligible subjects will be randomized 1:1:1 to receive EXPAREL (n=20), EXPAREL admixed with 0.25% bupivacaine HCl (n=20), or bupivacaine HCl (n=20). All subjects will receive combined sciatic (in the popliteal fossa) and saphenous (in the adductor canal) nerve blocks, by stratifying by each surgery grouping.
		

Treatments for Cohort 1 and Cohort 2
		

On the day of surgery, Cohort 1 and 2 subjects will receive ultrasound-guided combined sciatic (in popliteal fossa) and adductor canal nerve block with one of the following treatments:
		

 • EXPAREL arm: subjects randomized to this treatment arm will receive 20 mL (266 mg) EXPAREL mixed with 20 mL saline • EXPAREL admix arm: subjects randomized to this treatment arm will receive 20 mL (266 mg) EXPAREL admixed with 20 mL (50 mg) 0.25% bupivacaine HCl • Bupivacaine HCl arm: subjects randomized to this treatment arm will receive 40 mL (100 mg) 0.25% bupivacaine HCl 		

Block procedure:
		

Subjects may be lightly sedated with 1 to 2 mg of midazolam intravenously (IV) before the block procedure. The study drug (EXPAREL, EXPAREL admixed with 0.25% bupivacaine HCl, or bupivacaine HCl) will be administered under ultrasound guidance 90 min (±30 min) prior to surgery.
		

For all arms, the total volume (40 mL) will be split such that 20 mL will be administered as the sciatic nerve block (in popliteal fossa) and 20 mL will be administered as the saphenous nerve block (in the adductor canal).
		

Name of Sponsor/Company: Pacira Pharmaceuticals, Inc. [name] [contact]
	
Individual Study Table Referring to Part of the Dossier Volume: Page:
	
(For National Authority Use Only)

Name of Finished Products: EXPAREL® (bupivacaine liposome injectable suspension)
		

Name of Active Ingredients: Bupivacaine, 1.3%, 13.3 mg/mL
		

Study Schema:

Note: Cohort 1 will enroll bunionectomy subjects only.

Breakthrough Pain Medication:

All opioid and other analgesics (pain medications) administered post-surgery through Post-operative Day (POD) 14 should be recorded.

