9.7.2. Motor Function

Time to onset of motor block from end of study drug administration and duration of motor block will be summarized by the median and quartiles estimated using the Kaplan-Meier method similar to Section 9.5.2.2. Cumulative subject incidence plot (1 - [minus] Kaplan-Meier curves) will also be presented.

The number (and %) of subjects with complete motor function and partial/no motor function will be tabulated by treatment group and timepoint. Missing assessment will be imputed by LOCF.

Additionally, PD plot similar to the one described in Section 9.7.1 will be created for the sciatic distal and saphenous distal sensory nerves.

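### SAP 6.3.1 and 6.3.2 count block onset with no time limit but censor never-blocked subjects before surgery, which inflates the Kaplan-Meier onset estimate when an onset is first seen after surgery

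*SAP*

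**What the plan says.** SAP 6.3.1 defines sensory onset, separately for the sciatic and saphenous nerves, as the first time with "loss of EITHER light touch sensation OR cold sensation in EITHER proximal OR distal locations at any time". The next sentence gives the rule for subjects without onset: "If onset time is not achieved, it will be considered censored at the last onset assessment time prior to surgery".

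SAP 6.3.2 treats motor block in the same way. "Onset of motor block will be defined as the earliest timepoint with 2-point score of 1- Partial or no foot movement", with no upper time limit stated. For subjects who never lose motor function, "their onset will be censored at their last available motor assessment time point prior to surgery".

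Assessments do not stop at surgery. Both subsections schedule checks at "predose, 15 min, 30 min, 45 min, 1 h, 2 h, 8 h, 12 h, 24 h, 30 h" and onward to 168 h after the end of the block. Note c to the PK/PD schedule (Table 2) excludes checks while the subject is in surgery. SAP 9.2.5 refers back to 6.3.1 and 6.3.2 for censoring and adds nothing.

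Time to onset is a PD endpoint (Protocol 12.8, SAP 8.4). SAP 9.7.1 and 9.7.2 report it as Kaplan-Meier median and quartiles. For motor block, 9.7.2 adds: "Cumulative subject incidence plot (1 - [minus] Kaplan-Meier curves) will also be presented".

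**The concern.** A subject can be classed as never blocked only by looking at the whole set of checks, including those after surgery. The SAP uses that knowledge to decide who is censored, but places the censoring time before surgery. A subject whose block is first seen after surgery stays at risk until that check. A subject examined at the same check and found unblocked has already left the risk set. Censoring therefore depends on the later outcome, and the Kaplan-Meier assumption of non-informative censoring fails.

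The trigger is foreseeable. Study drug "will be administered under ultrasound guidance 90 min (±30 min) prior to surgery", and no checks are made during surgery, so a block that sets in around or during surgery is first recorded afterwards. What is at stake is the description of block onset and block success in Cohort 1, above all the motor cumulative incidence plot.

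**Working it through.** **Inputs from the documents.** Time 0 is the end of study drug administration (SAP 5). Surgery starts 90 ± 30 min after the block, that is 60 to 120 min. Scheduled checks are at 15, 30 and 45 min, 1 h, 2 h, 8 h and on to 168 h. Cohort 1 plans 20 subjects per arm. The documents give no onset pattern or block-failure rate, so there is no figure to reproduce, and the patterns below are assumptions.

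**Formula.** S(t) is the product of (1 − d/r) over event times, with d onsets and r subjects at risk. Reported incidence is 1 − S(t).

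**Set-up.** Early onsets are at 0.25, 0.5 and 0.75 h, and late onsets at 8 h. Never-blocked subjects are censored at 1 h (SAP rule) or kept at risk to their last check, taken as 168 h.

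| Early / at 8 h / never | S after early onsets | S at 8 h, SAP rule | S at 8 h, kept at risk | Incidence: SAP vs kept |
|---|---|---|---|---|
| 16 / 1 / 3 | 4/20 = 0.20 | 0.20 × (1 − 1/1) = 0 | 0.20 × (1 − 1/4) = 0.15 | 100% vs 85% |
| 12 / 2 / 6 | 8/20 = 0.40 | 0.40 × (1 − 2/2) = 0 | 0.40 × (1 − 2/8) = 0.30 | 100% vs 70% |
| 8 / 1 / 11 | 12/20 = 0.60 | 0.60 × (1 − 1/1) = 0 | 0.60 × (1 − 1/12) = 0.55 | 100% vs 45% |
| 18 / 0 / 2 | 2/20 = 0.10 | no event | no event | 90% vs 90% |

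The kept-at-risk figure equals the observed proportion blocked in every row.

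**Median and quartiles**, taken as the first time incidence reaches 50% or 75%, with one late onset:

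- 16/1/3: median 0.5 h and upper quartile 0.75 h under both rules.
- 14/1/5: upper quartile 8 h under both, since 0.30 × 5/6 = 0.25.
- 13/1/6: upper quartile 8 h under the SAP rule. Kept at risk it is not reached, since 0.35 × 6/7 = 0.30 gives 70%.
- 9/1/10: median 8 h under both, since 0.55 × 10/11 = 0.50.
- 8/1/11: median 8 h under the SAP rule and not reached when kept at risk (45%).

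The upper quartile therefore changes from 6 failures in 20, and the median from 11.

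**When 100% is not forced.** Take 16 early onsets, two never-blocked subjects censored at 1.0 h, a third censored at 2.0 h, and one onset first seen at 1.5 h. Two are at risk at 1.5 h, so S = 0.20 × (1 − 1/2) = 0.10 and incidence is 90%, against 85% with all kept at risk. The curve is inflated but does not reach 100%. That needs the last onset to fall after every pre-surgery censoring time.

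**Unequal censoring times before surgery.** Suppose 14 are blocked by 0.75 h (S = 0.30), 2 more have onset at 1 h, and one never-blocked subject is censored at 0.75 h. At 1 h the SAP rule gives S = 0.30 × 3/5 = 0.18 (82%), against 0.30 × 4/6 = 0.20 (80%). This effect is small.

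**The case against.** The strongest reply is that the SAP means onset to be sought only before surgery. It speaks of onset assessments before surgery and offset assessments after it. Its duration rule in 6.3.1 says that when onset is not achieved, duration runs from the start of surgery to offset. A subject with an offset must have been blocked, so onset not achieved seems there to mean not captured before surgery. SAP 9.5.2.4 fits this, since it treats such durations as shorter than the true ones. On that reading a block first seen after surgery is itself censored before surgery, the two periods match, and the 16/1/3 pattern gives 80% with no jump.

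This reading has real support, but it conflicts with counting sensory loss "in EITHER proximal OR distal locations at any time". Those words appear only for sensory onset. The motor definition lacks them, although the only planned incidence plot is motor. The motor text nevertheless sets no time limit, so two programmers could derive 80% or 100% from the same data. The need to reconcile the text stands on either reading.

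Three other points stand:

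- A reader might infer that block failures vanish from the report. They do not. SAP 9.7.1 and 9.7.2 tabulate numbers and percentages by timepoint for sensory and motor function, and 9.7.1 plots the percentage with motor block on.
- A reader might infer that one post-surgery onset always forces 100%. The 1.5 h example shows otherwise.
- Checks stop after two consecutive evaluations at predose level. The SAP does not say how this applies to a subject never blocked, so follow-up to 168 h cannot be assumed for everyone.

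**Conclusion.** The event and censoring rules for block onset cover different periods. Read literally, they give informative censoring that inflates the Kaplan-Meier onset estimate. The inflation is 15 percentage points in the 16/1/3 pattern (100% against 85%). It is 30 points with 6 failures and two late onsets, and 55 points with 11 failures and one late onset. All these patterns are assumed, and the documents do not show how likely any of them is.

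The main effect is on the motor one-minus-Kaplan-Meier plot. With few failures and one late onset the median and quartiles do not move. If no onset is first seen after surgery there is no jump at the end of the curve. The rules then agree when never-blocked subjects share one censoring time, and can differ slightly when they do not.

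A reader might also infer that treatment comparisons or the trial's efficacy conclusions are biased. The documents do not support that. Time to onset is a descriptive PD summary in Cohort 1, no test of onset is named in 9.7.1 or 9.7.2, and onset is outside the testing hierarchy in SAP 9.5. No confirmatory conclusion is affected. The point is still worth correcting, because the estimator is wrong under the literal text and the correction is small.

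**What to change.** Choose one period for events and censoring, and state it in both 6.3.1 and 6.3.2:

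- (a) Count onset at any assessment. Censor subjects with no observed onset at the last assessment, including those after surgery, at which block status was recorded. Tying censoring to recorded status also covers subjects whose checks ended early.
- (b) Count onset only at pre-surgery assessments, and censor everyone else, including subjects whose block is first seen after surgery, at the last pre-surgery assessment.

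Under either option, make the duration rule in 6.3.1, which 6.3.2 adopts for motor block, use the same meaning of onset not achieved. Report the number and percentage of subjects with no onset per arm beside the Kaplan-Meier summaries.

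The cost is about one sentence in each of two SAP subsections, matching words in the duration rule, one derivation line and one table row. No new data are needed. Where blocks fail, reported incidence may look less favourable.

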12. STUDY ENDPOINTS AND MEASUREMENTS

12.1. Efficacy Assessments

- Pain intensity measured using the NRS as “How much pain are you experiencing right now?” will be assessed:
 - Upon arrival in the Post-anesthesia Care Unit (PACU) (± 5 min)

- Every 15 minutes in the PACU (± 5 min)
- At PACU discharge (± 5 min)
- Every 6 hours from the end of surgery until 96 hours post-surgery: 6 h (± 2 h), 12 h (± 2 h), 18 h (± 2 h), 24 h (± 2 h), 30 h (± 2 h), 36 h (± 2 h), 42 h (± 2 h), 48 h (± 2 h), 54 h (± 2 h), 60 h (± 2 h), 66 h (± 2 h), 72 h (± 2 h), 78 h (± 3 h), 84 h (± 3 h), 90 h (± 3 h), and 96 h (± 3 h)
- An unscheduled NRS assessment will be obtained immediately prior to administration of any breakthrough pain medication until 96 hours post-surgery.
- Pain intensity using the NRS once daily at 21:00 (± 3 h) from POD 1 to POD 14 measured as “What was your **worst** pain in the last 24 hours?”
- Pain intensity using the NRS once daily at 21:00 (± 3 h) from POD 1 to POD 14 measured as “What was your **average** pain in the last 24 hours?”
- In addition, subject satisfaction with pain management using 1 question from the International Pain Outcome (IPO) questionnaire will be recorded at 96 hours (± 3 h) post-surgery.

Subjects will be instructed to focus all NRS pain intensity ratings on the operative ankle/foot, and not other locations where they may be experiencing pain.

The following information shall be captured for data management purposes:

- Start and end time of block
- Start and stop time of surgery
- Start and stop of PACU admission and discharge
- Date and time of health care facility admission and discharge

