Duration of motor block will be analyzed by the Kaplan-Meier survival analysis. Although duration can be captured as left, right, or interval censored (Section 6.3.1), all these censored durations will be considered right censored for the programming purpose, because all these censoring implies that the actual duration is longer than the observed censored duration. Median time and the stratified log-rank test comparing EXPAREL and EXPAREL admixed with 0.25% bupivacaine HCl will be presented.

In addition to the presentation of the median, the ratio of EXPAREL to 0.25% bupivacaine HCl in motor duration median will be presented. The ratio is derived as follows,

 $Ratio = (Median_{EXPAREL}/Median_{EXP+Bup})$

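### Motor-block offset is dated to the first recovered visit and used as an exact time on a grid with 12 to 24 h gaps, which biases the median durations upward and can distort the EXPAREL/admix ratio

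*SAP*

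**What the plan says.** Motor function is tested in Cohort 1 only, about 20 subjects per arm (Protocol 11.1). After the early tests, SAP 6.3.2 schedules it at "8 h, 12 h, 24 h, 30 h, 48 h, 60 h, 72 h, 84 h, 96 h", then at 120, 144 and 168 h from the end of the block. Testing stops once recovery is confirmed on two consecutive tests.

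Offset is the "first time point of the two consecutive recovery assessments". Duration "will be defined as time between onset and offset of motor block".

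SAP 9.5.2.4 then states: "Duration of motor block will be analyzed by the Kaplan-Meier survival analysis". It adds a stratified log-rank test of EXPAREL against the admix and says that a ratio "in motor duration median will be presented". The formula under that sentence is the EXPAREL median over the admix median.

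This is the fourth secondary endpoint and the last step of the hierarchy in SAP 9.5. Median block durations are also PD endpoints (Protocol 12.8), summarised by Kaplan-Meier in SAP 9.7.

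**The concern.** The first recovered test marks the right-hand end of an interval, not the time of recovery. Between "12 h, 24 h, 30 h, 48 h, 60 h, 72 h, 84 h, 96 h" a block can wear off up to 18 h before anyone tests the foot, yet the analysis treats the test time as the recovery time.

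Nothing in the plan corrects for this. The interval-censored label in SAP 6.3.1 is for durations whose onset and offset were not captured, not for recovery between two visits, and SAP 9.5.2.4 handles all censored durations as right censored. The extra tests are optional and directed at onset: "Additional unscheduled assessments may be performed, particularly around the surgery if no onset of block is noted". No interval-censored or sensitivity analysis is planned for this endpoint.

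At stake is the description of how long the block lasts and how EXPAREL compares with the admix. A reader will take the medians and their ratio as the clinical summary of a stated secondary objective.

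**Working it through.** **Plan's own figure.** There is none to reproduce. The sample-size section covers only the primary AUC endpoint, and neither document gives an expected duration, spread or precision for motor block.

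**Inputs.** The visit grid and offset rule are from SAP 6.3.2, the visit windows from Protocol 12.7 (±30 min at 12 h; ±1 h at 24, 30 and 48 h; ±2 to ±3 h later), and n = 20 per arm from Protocol 11.1. True medians and log-SDs are assumptions.

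**Step 1: gaps.** 24 − 12 = 12 h; 30 − 24 = 6 h; 48 − 30 = 18 h; 12 h between each pair of visits from 48 to 96 h; 24 h between each pair from 96 to 168 h. The windows do not fill these gaps.

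**Step 2: shift of a median.** Recorded offset = first scheduled visit at or after the true offset (nominal times, onset error ignored).

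| True median (h) | Recorded (h) | Shift |
|---|---|---|
| 13 | 24 | +11 h (85%) |
| 20 | 24 | +4 h (20%) |
| 31 | 48 | +17 h (55%) |
| 40 | 48 | +8 h (20%) |
| 47 | 48 | +1 h (2%) |
| 70 | 72 | +2 h (3%) |
| 100 | 120 | +20 h (20%) |

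**Step 3: effect on the ratio.** If each sample median equalled the true one, 31/47 = 0.66 would be reported as 48/48 = 1.00, and 29/32 = 0.91 as 30/48 = 0.63. These are limiting cases. Simulated typical (median) ratios follow, with 20 per arm, log-normal durations, 1,500 runs per scenario and visits varied within the protocol windows:

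| True medians (h) | log-SD | Exact times | Planned grid |
|---|---|---|---|
| 29 vs 32 | 0.3 | 0.91 | 0.65 |
| 29 vs 32 | 0.5 | 0.90 | 0.98 |
| 31 vs 47 | 0.3 | 0.66 | 0.80 |
| 31 vs 47 | 0.5 | 0.66 | 0.65 |
| 40 vs 60 | 0.3 | 0.67 | 0.78 |
| 70 vs 90 | 0.3 | 0.78 | 0.77 |

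Precision is affected too. With equal arms at 31 h (log-SD 0.3), the 5-95% range of the ratio widens from 0.82-1.21 to 0.64-1.57. At 40 h it collapses from 0.83-1.21 to 0.98-1.02, which is false precision.

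**Step 4: the test.** In the same runs (unstratified log-rank), rejection with equal arms was about 5 to 6.5% with exact times and on the grid alike. Power loss was mostly 0 to 5 points. The largest was from 70% to 58% (20 vs 26 h, log-SD 0.3).

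**Step 5: does an analysis-only change help?** A second set of simulations used nine pairs of medians at log-SD 0.3, 0.4 and 0.6 (27 settings, 3,000 trials each, nominal visit times). The planned method overstated the EXPAREL median by 2.6 to 11.6 h on average; with visits varied within windows the range was about 3 to 11.5 h. Placing the median by linear interpolation inside its interval, on the unchanged grid, cut the mean bias to between −0.1 and +1.3 h. The RMSE of the log ratio fell in 26 of 27 settings and did not improve in the other. At 32 vs 46 h it fell from 0.285 to 0.152 (exact times: 0.158), and the typical ratio became 0.70, which is the true value (32/46 = 0.70).

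**The case against.** A reader might infer three stronger things, none of which the documents support.

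- **That the medians and ratio largely reflect the visit grid.** The documents give no durations or spread from which to show this. The distortion is small when a median falls just before a visit (47 or 70 h in Step 2), and at 70 vs 90 h the ratio is almost unchanged. Nor would exact ties be common: actual times are recorded and onset is subtracted, so a ratio of exactly 1 arises mainly if every visit is assumed to occur at its nominal hour.
- **That the last test in the hierarchy is compromised.** The planned comparison is the stratified log-rank; the ratio is only presented. Both arms are tested on one schedule, and Step 4 shows the error rate holding.
- **That more bedside tests are needed.** Pain is already scored "Every 6 hours from the end of surgery until 96 hours post-surgery", so adding a foot test at 18, 36 and 42 h looks easy. But it would amend the protocol after enrolment had begun (SAP 5 and 6.4), put subjects on mixed schedules, call on the limited pool of trained licensed assessors in Protocol 12.7, and leave the gaps after 48 h as they are. SAP 6.4 shows what a mid-study change can cost: six subjects are excluded from the sensory-block evaluation. Step 5 shows that the analysis can do the work without new tests.

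These points limit the concern but do not remove it. The upward bias in the medians and the possible distortion of the ratio remain, with nothing planned to correct them.

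A further fair point is that a Turnbull estimate alone does not locate a median inside a gap. The fix must therefore state a convention.

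**Conclusion.** The concern holds for estimation, not for the hypothesis test. Reported median motor-block durations will be biased upward, by about 3 to 11.5 h under the assumptions used: log-normal durations, medians 20 to 80 h, log-SD 0.3 to 0.6, 20 per arm, no missed visits, onset error ignored. The EXPAREL/admix ratio of medians may be close to right, pulled towards 1 or pushed away from it, depending on where the true medians fall relative to the visits. That cannot be settled from the documents. The log-rank comparison stays essentially valid, with mostly small power loss. This is a worthwhile improvement to a descriptive result of a late secondary endpoint, not a flaw that threatens the trial's conclusions.

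**What to change.** Before unblinding, amend SAP 9.5.2.4, and SAP 9.7 for the PD median durations, as follows:

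- Treat each observed offset as lying between the last blocked and the first recovered assessment, using actual times.
- Estimate the medians and their ratio with an interval-censored method and a stated within-interval convention: for example Turnbull with linear interpolation, or a parametric interval-censored model.
- Report these with confidence intervals beside the planned Kaplan-Meier medians.
- Keep the stratified log-rank test as the hierarchical comparison, and leave the visit schedule unchanged.

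While editing 9.5.2.4, reconcile the sentence introducing the ratio, which names bupivacaine HCl as the comparator, with its formula, which uses the admix.

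The cost is SAP wording and some programming, with no new data. The small downside is that the estimate relies on the interpolation or parametric assumption inside a gap; showing both sets of medians makes that reliance visible.
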